9.3. Populations for Analyses

For purposes of analysis, the following populations are defined:

Population	Description	
Enrolled Set	All participants who signed the ICF and passed Screening.	
Full Analysis Set	The primary statistical analysis will be based on the Full Analysis Set, which is defined as all participants who received at least one dose of PD-0325901 (mirdametinib).	
Per-Protocol Set	A Per-Protocol population, defined as a subset of the Full Analysis Set who have completed a minimum of disease evaluations and who do not have any major deviations, including but not limited to efficacy assessments or compliance, will be used to analyze a set of analysis considered supportive to the primary efficacy analyses.	
Safety Set	All participants assigned to study treatment and who took at least one dose of study treatment.	

9.4. Statistical Analyses

The statistical analysis plan will be developed and finalized before database lock and will describe the participant populations to be included in the analyses, and procedures for accounting for missing, unused, and spurious data. This section is a summary of the planned statistical analyses of the primary and secondary endpoints. As stated in Section 9.2 above, the primary and secondary endpoints in the pediatric and adult cohorts will be analyzed separately since each cohort is age-dependent. Other secondary endpoints may be pooled, if appropriate to the endpoint.

9.4.1. Efficacy Analyses

Endpoint	Statistical Analysis Methods
Primary	The primary endpoint is objective response rate (ORR) at the end of the Treatment Phase, defined as the proportion of participants who have a \geq 20% reduction in target tumor volume as compared to Baseline. Exact 1-sided binomial 95% confidence intervals will be calculated on the response rate. Participants who are missing all response data will be treated as non-responders. Participants who discontinue early from the study without responding will be treated as non-responders. Objective response rate will be calculated separately by age cohort.
Secondary	Duration of response (DOR) in participants who meet the criteria for ORR will be calculated as the time between the first instance of response until the date of progression or censored date (censorship rules will be specified in the analysis plan). The DOR will be analyzed using Kaplan Meier method; median duration of response and the 95% CIs on the intervals will be calculated. Kaplan Meier will be used for the overall population, and also on cohort groups. Details of censoring methods and sensitivity analyses will be described in the statistical analysis plan.
	Time-to-Response will also be calculated as the time between first dose and the first date of objective response. Univariate statistics will be reported.
	Change from baseline in overall clinical status: All participants and/or parents/legal representatives will complete a HRQOL (PedsQL) to assess overall change in clinical status.
	Change from baseline in pain: Pain will be measured using an 11-point numeric rating scale (NRS-11) and the Pain Interference Index. For the NRS-11, participants will report overall pain in the location of the primary target tumor. The Pain Interference Index questionnaire will assess self-reported and parent/legal representative reported consequences of pain on relevant aspects of one's life over the previous 7-day period.
Exploratory	Progression Free Survival is defined as the time in months from the first dose to the date of a \geq 20% increase in tumor volume or death. Participants who do not meet the criteria for progression will be censored (censorship rules will be specified in the analysis plan). The PFS will be analyzed using Kaplan Meier methods; median PFS and the 95% CIs on the intervals will be calculated. Details of censoring methods and sensitivity analyses will be described in the statistical analysis plan.
	Change from baseline in functional assessments: In participants who have tumors that affect functional status at Baseline, the change from Baseline in

muscle strength and range-of-motion in the PN affected areas will be measured. Participants with a target PN causing airway or lower extremity motor dysfunction at Baseline will be assessed for change in 6-minute walk test distance. Participants and/or parents/legal representatives-reported questionnaires (e.g., PROMIS) will be assessed for change in functionality and mobility.

Self-reported overall severity of symptoms and status (e.g., PGIS, PGIC) will also be assessed.

Self-reported and observer-reported acceptability (e.g., P-OMAQ) of the dispersible tablet (pediatric formulation) will be assessed.

Additional exploratory endpoints will be described in the statistical analysis plan finalized before database lock.

9.4.2. Safety Analyses

All safety analyses will be performed on the Safety Population.

Endpoint	Statistical Analysis Methods
Safety Endpoints	The safety and tolerability of mirdametinib (PD-0325901) will be evaluated by means of study drug-related adverse event reports, physical examinations, and laboratory safety evaluations. National Cancer Institute CTCAE Version 5.0 will be used for grading of adverse events. Investigators will provide their assessment as related to treatment (definite, probable, or possible relationship).
	The incidence of treatment-emergent adverse events, SAEs, adverse events of at least Grade 3 in severity, study drug-related adverse events, and adverse events leading to withdrawal of study drug will be summarized. Treatment-emergent adverse events will be those that start or worsen on or after the first day of study drug through 30 days after the last dose of study drug; related adverse events will be those with an Investigator determination of related to treatment.
	Laboratory data will be analyzed by summary statistics over time, as well as by shift tables based on NCI CTCAE Version 5.0 grades of severity. In addition, ECG intervals will be summarized by visit. The number and percentage of participants who have a post-Baseline QTcF between 450 and 480, > 480, and > 500, as well as the number and percentage of participants who have a change from Baseline in QTcF of < 30, 30 to 60, and > 60 will be summarized.

9.4.3. Other Analyses

Pharmacokinetic, pharmacodynamic, and biomarker exploratory analyses will be described in the statistical analysis plan finalized before database lock. The population PK analysis and pharmacodynamic analyses will be presented separately from the main clinical study report.

9.5. Data Monitoring Committee (DMC)

This study will utilize an independent data monitoring committee (DMC) and will operate according to an established charter. The committee will be composed of 3 members including physicians knowledgeable in the treatment of NF1 and an independent statistician. Sponsor employees will not be members of the DMC. The DMC will be responsible for ongoing monitoring of the safety, efficacy and benefit/risk profile of participants in the Treatment Phase of the study. Reviews will include aggregate safety, targeted medical events of special interest, serious AE data and aggregate endpoint data.

Following each data review, the DMC may recommend 1) no changes to the study are needed, 2) changes to the protocol or informed consent/assent based on clinical safety findings, or 3) early termination of the study based on safety analyses. The recommendations made by the DMC to alter the conduct of the study will be forwarded to the Sponsor for final decision. Additionally, the DMC may be asked to assist the Sponsor in evaluating the impact of data from other company-sponsored studies or other published studies.

The DMC charter will outline the frequency of meetings and detail all aspects of DMC's scope of review and procedures.

In addition to routine scheduled meetings as described in the DMC charter, the DMC will also convene after the first 5 participants aged 9 to 17 years in the pediatric cohort have completed at least 2 cycles of study treatment. The DMC will evaluate cumulative safety data for these 5 participants and based on these data, will determine further enrollment requirements for the pediatric cohort, potentially expanding enrollment of the pediatric cohort to include participants aged 2 to 17 years of age.

10. Supporting Documentation and Operational Considerations

10.1. Appendix 1: Regulatory, Ethical, and Study Oversight Considerations

10.1.1. Regulatory and Ethical Considerations

This study will be conducted in accordance with the protocol and with the following:

- Consensus ethical principles derived from international guidelines including the Declaration of Helsinki and Council for International Organizations of Medical Sciences International Ethical Guidelines;
- Applicable International Council for Harmonisation (ICH) Good Clinical Practice (GCP) Guidelines; and
- Applicable laws and regulations.

The protocol, protocol amendments, informed consent/assent form (ICF), Investigator Brochure, and other relevant documents (e.g., advertisements) must be submitted to an institutional review board/independent ethics committee (IRB/IEC) by the Investigator and reviewed and approved by the IRB/IEC before the study is initiated.

Any amendments to the protocol will require IRB/IEC approval before implementation of changes made to the study design, except for changes necessary to eliminate an immediate hazard to study participants.

The Investigator will be responsible for the following:

- Providing written summaries of the status of the study to the IRB/IEC annually or more frequently in accordance with the requirements, policies, and procedures established by the IRB/IEC;
- Notifying the IRB/IEC of serious adverse event or other significant safety findings as required by IRB/IEC procedures; and
- Providing oversight of the conduct of the study at the Site and adherence to requirements of 21 Code of Federal Regulations (CFR), ICH guidelines, the IRB/IEC, European regulation 536/2014 for clinical studies (if applicable), and all other applicable local regulations.
- The Investigator will be responsible for reporting cases of suspected child abuse and/or neglect according to local medical association (e.g., AAP) or health department guidelines.

10.1.2. Financial Disclosure

Investigators and sub-investigators will provide the Sponsor with sufficient, accurate financial information as requested to allow the Sponsor to submit complete and accurate financial certification or disclosure statements to the appropriate regulatory authorities. Investigators are

responsible for providing information on financial interests during the course of the study and for 1 year after completion of the study.

10.1.3. Informed Consent/Assent Process

- The Investigator or their representative will explain the nature of the study to the participant or their legally authorized representative and answer all questions regarding the study.
- Participants must be informed that their participation is voluntary. Participants or their legally authorized representative (parent/guardian) will be required to sign a statement of informed consent/assent that meets the requirements of 21 CFR 50, local regulations, ICH guidelines, Health Insurance Portability and Accountability Act requirements, where applicable, and the IRB/IEC or study center.
- The medical record must include a statement that legally authorized representative (parent/guardian) consent and child/adolescent assent (if deemed appropriate by local ethics review) was obtained before the participant was enrolled in the study and the date the written consent/assent was obtained. The medical record should also describe how the clinical Investigator determined that the person signing the ICF was the participant's legally authorized representative (parent/guardian). The authorized person obtaining the informed consent/assent must also sign the ICF.
- Participants and their legally authorized representative (parent/guardian) must be reconsented/assented to the most current version of the ICF(s) during their participation in the study.
- Minor participants must be re-consented if they reach the age of majority during the course of the study, in order to continue participating.
- A copy of the ICF(s) must be provided to the participant or the participant's legally authorized representative.
- Consideration of rescreening of a participant who did not meet eligibility criteria must be discussed with the Medical Monitor. The participant must be re-consented/assented if approved for rescreening. In addition, all Screening assessments must be repeated with the exception of imaging, which would only be repeated if the imaging assessment was obtained > 45 days from the first dose of study treatment.

10.1.4. Data Protection

Participants will be assigned a unique identifier by the Sponsor. Any participant records
or datasets that are transferred to the Sponsor will contain the identifier only; participant
names or any information which would make the participant identifiable will not be
transferred.

- The participant must be informed that his/her personal study-related data will be used by the Sponsor in accordance with local data protection law. The level of disclosure must also be explained to the participant.
- The participant must be informed that his/her medical records may be examined by Clinical Quality Assurance auditors or other authorized personnel appointed by the Sponsor, by appropriate IRB/IEC members, and by inspectors from regulatory authorities.

10.1.5. Data Quality Assurance

- All participant data relating to the study will be entered into the electronic case report forms (eCRFs) unless transmitted to the Sponsor or designee electronically (e.g., laboratory data). The Investigator is responsible for verifying that data entries are accurate and correct by electronically signing the eCRF.
- The Investigator must maintain accurate documentation (source data) that supports the information entered in the eCRF.
- The Investigator must permit study-related monitoring, audits, IRB/IEC review, and regulatory agency inspections and provide direct access to source data documents.
- Monitoring details describing strategy methods, responsibilities and requirements, including handling of noncompliance issues and monitoring techniques (central, remote, or on-site monitoring) will be indicated in the monitoring plan to ensure the protocol and GCP is followed.
- The Sponsor or designee is responsible for the data management of this study including quality checking of the data.
- The Sponsor assumes accountability for actions delegated to other individuals (e.g., Contract Research Organizations).
- Study monitors will perform ongoing source data verification to confirm that data
 entered into the eCRF by authorized Site personnel are accurate, complete, and
 verifiable from source documents; that the safety and rights of participants are being
 protected; and that the study is being conducted in accordance with the currently
 approved protocol and any other study agreements, ICH GCP, and all applicable
 regulatory requirements.
- Records and documents, including signed ICFs, pertaining to the conduct of this study must be retained by the Investigator according to specifications in the ICH guidelines, local regulations, or as specified in the clinical trial agreement, whichever is longer. No records may be destroyed during the retention period without the written approval of the Sponsor. No records may be transferred to another location or party without written notification to the Sponsor.

10.1.6. Source Documents

- Source documents provide evidence for the existence of the participant and substantiate the integrity of the data collected. Source documents are filed at the Investigator's Site.
- Data reported in the eCRF that are transcribed from source documents must be consistent with the source documents or the discrepancies must be explained. The Investigator may need to request previous medical records or transfer records, depending on the study. Also, current medical records must be available.
- Investigators will maintain records separate from the eCRFs in the form of clinical charts, medical records, original laboratory, radiology and pathology reports, pharmacy records, etc. The Investigator will document in the clinic chart or medical record the date on which the participant signed informed consent/assent prior to participation in the study. Source documents must completely reflect the nature and extent of the participant's medical care and must be available for source document verification against entries in the eCRFs when the Sponsor's monitor visits the Site. In order to meet data integrity requirements, source documentation should be attributable, legible, contemporaneous, accurate, available/accessible, original, complete and credible. All information obtained from these documents will be kept in strict confidentiality. Definition of what constitutes source data can be found in the study reference manual.

10.1.7. Study and Site Closure

The Sponsor reserves the right to suspend or terminate the study at any time for any reason at the sole discretion of the Sponsor. Reasons which would cause the Sponsor to suspend/terminate enrollment include, but are not limited to, the occurrence of any of the following:

- One Grade 5 AE;
- Two Grade 4 AEs;
- One occurrence of any of the following ocular toxicities: retinal vein occlusion, unexplained Grade 3+ Optic Neuropathy, Grade 3+ retinal vein detachment, or unexplained Grade 3+ retinopathy;
- Two absolute decreases in LVEF > 20% from Baseline of the Treatment Phase or symptomatic congestive heart failure not explained by any other cause; or
- One participant meeting QTc stopping criteria as described in Section 7.1.2.

Study Sites will be closed upon study completion. A study Site is considered closed when all required documents and study supplies have been collected, a study Site closure visit has been performed, and the IRB has been notified of closure.

Study Site closure prior to completion of the study should be avoided. The Investigator and Sponsor will agree to the circumstances that could cause early study Site closure.

The Sponsor reserves the right to close the study Site at any time for any reason at the sole discretion of the Sponsor. Reasons for the early closure of a study Site by the Sponsor or Investigator may include but are not limited to:

- Failure of the Investigator to comply with the protocol, the requirements of the IRB/IEC or local health authorities, the Sponsor's procedures, or GCP guidelines;
- Inadequate recruitment of participants by the Investigator; or
- Discontinuation of further study treatment development.

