6.6. Dose Modification

Every effort should be made to administer study treatment at 2 mg/m² BID; however, in the event of significant toxicity, dosing must be interrupted and/or dose reduced as described in Table 4 and Table 5.

Interruption of study treatment should continue until the toxicity is resolved to \leq Grade 1 or Baseline. An interruption of study treatment for more than 14 days due to any toxicity may require permanent discontinuation. After 14 days of interruption, study treatment may be resumed only after discussion with the Medical Monitor and approval by the Sponsor. Refer to Section 10.10.3 for the Medical Monitor contact details.

After interruption, study treatment may be resumed at a reduced dose as described in Table 4 and Table 5. Should the same Grade toxicity recur at the reduced dose and the AE is considered related to the study treatment, the participant may be discontinued at the discretion of the Investigator, pursuant to discussion with the Medical Monitor and Sponsor. Following a dose reduction, an increase in the study treatment dose due to a BSA change is permitted at the discretion of the Investigator with approval from the Medical Monitor and Sponsor.

An unscheduled visit may be performed at any time during the study. Assessments to be performed at the visit will be determined by the Investigator.

Table 4 Criteria For Dose Modification For Study Drug Related Adverse Events

RELATED ADVERSE EVENTS	INTERVENTION
OCULAR/VISUAL	
Any Grade ≤ 2 event.	Continue dosing and perform ophthalmologic exams every 2 to 4 weeks until resolution to Grade ≤ 1 or baseline.
Any Grade ≥ 3 event except RVO.	Interrupt dosing; if resolution to Grade ≤ 1 or baseline occurs within 14 days, re-start study treatment at the next lower dose following Table 5. Consider ophthalmologic exams every 2 to 4 weeks.
Grade ≥ 3 retinal vein occlusion (RVO)	Permanently discontinue study treatment
NEUROLOGICAL	
Grade ≤ 2 events such as hallucination, confusion or delirium lasting more than 24 hours AND after ruling out other possible causes.	Interrupt dosing; if resolution to Grade ≤ 1 or baseline occurs within 14 days, re-start study treatment at the next lower dose following Table 5.
Any Grade ≥ 3 event.	Withhold dose and discuss with the Medical Monitor. Consider permanent discontinuation after re-evaluating the benefit risk of ongoing study drug treatment
MUSCULOSKELETAL	

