7.1. Discontinuation of Study Treatment

It may be necessary for a participant to permanently discontinue study treatment prematurely or for the Sponsor to suspend study enrollment.

Participants who permanently discontinue from the Treatment Phase prior to the Cycle 24 visit will be required to return to the clinic for an early termination (ET) visit as close as possible to the last dose of study treatment (PD-0325901, mirdametinib). Participant will also be required to return for a Safety Follow-Up visit (30 days [+5 days] after the last dose of study drug) (refer to the SoA in Section 1.3 for timing and a complete list of required assessments to be conducted).

Conditions upon which the Sponsor will suspend additional enrollment in the study are described in the specified stopping criteria in Section 10.1.7.

Reasons for discontinuation of study treatment early may include:

[figure not shown]
- Participants who meet the definition of progressive disease (a ≥ 20% increase in the volume of the target PN as compared to the Treatment Phase Baseline [Section 10.7], confirmed by central radiologic review);
- Occurrence of any medical condition or circumstance that exposes the participant to substantial risk and/or does not allow the participant to adhere to the requirements of the protocol.
- Any SAE (refer to Section 10.3.2 for SAE criteria), clinically significant AE (refer to QTc stopping criteria below; Section 7.1.2), severe laboratory abnormality (refer to liver chemistry stopping criteria below; Section 7.1.1), intercurrent illness, RVO, or other medical condition which indicates to the Investigator that continued participation is not in the best interest of the participant;
- Pregnancy (refer to Sections 8.3.6 and 10.4 for additional details);
- Requirement of prohibited concomitant medication (Section 6.5.2);
- Participant failure to comply with protocol requirements or study-related procedures; or
- Termination of the study by the Sponsor as described in Section 10.1.7, the IRB or the regulatory authority.

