8.3.1. Adverse Events of Special Interest

Table 10 Adverse Events of Special Interest (AESI)

Gastrointestinal (reported as AESI if Grade ≥ 3)			
Diarrhea	Nausea Vomiting		
Eye Disorders (reported as AESI if Grade ≥ 2)			
Retinal Vein Occlusion (RVO)	Uveitis Optic neuropathy		
Retinopathy	Retinal detachment		
Cardiac Disorders (reported as AESI if Grade ≥ 2)			
Ejection fraction decreased	Cardiac failure Left ventricular dysfunction		
Neurologic Disorders (reported as AESI if Grade ≥ 2)			
Confusion	Hallucinations Delirium		
Skin Disorders (reported as AESI if Grade ≥ 3)			
Rash	Acneiform rash		

These are selected, non-serious AEs and SAEs that **must be reported within 24 hours** regardless of relationship to study treatment. For participants who experience signs or symptoms that may be consistent with an AESI, sites are strongly encouraged to immediately notify the Medical Monitor of the event via email and/or phone. Documentation of potential AESIs should occur after discussion between the investigator and the Medical Monitor. Many of these events may also qualify as SAEs. Any event that meets the criteria described in Table 10 must be reported regardless of investigator-determined relationship to study treatment (unless otherwise

specified). Investigators/study coordinators/designated site personnel are required to record these experiences in the eCRF (as described in the eCRF completion guidance document) and to provide supplemental information (such as medical history, concomitant medications, investigations, etc.) about the event. Please note this table lists known AESI, and additional events may be identified during the course of the study.

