If an abscess develops, surgical treatment with incision and drainage with or without debridement should be done. Any infectious organisms identified should be treated accordingly. If the participant has diabetes or is immune compromised, oral antibiotics ensuring coverage for staphylococcal aureus (see above) should be started prior to a culture and sensitivity report. Once culture report is obtained, the antibiotic therapy should be adjusted as appropriate.

Visual adverse events:

All participants will have a detailed ophthalmologic evaluation at Screening. In participants who develop visual symptoms, a repeat ophthalmologic evaluation will be performed to include: best corrected visual acuity, intraocular pressure, slit lamp fundoscopy (photograph if abnormal).

If a diagnosis of retinal pigment epithelial detachment or central serous retinopathy is made, treatment with PD-0325901 will be held and repeat ophthalmologic evaluations will be performed until resolution. Treatment may be restarted after complete resolution of symptoms to baseline.

If a diagnosis of retinal vein occlusion (RVO) is made, PD-0325901 will be discontinued permanently.

Gastrointestinal adverse events:

Diarrhea: Non-infectious diarrhea should be treated with loperamide. Additional agents may be used concurrently if loperamide is not adequate to control diarrhea as a single agent. In addition, the following dietary advice should be considered: BRAT diet (bananas, rice, apple sauce, toast, plain pasta), readily digestible food, avoidance of lactose-containing products and fried, fatty or spicy foods, increased fluid intake (8-10 glasses of clear fluids/day (including water, clear broth, fluids containing salt and sugar). Participants should be encouraged to seek advice early from their physician or study nurse if they have persistent diarrhea, diarrhea complicated by vomiting, or inability to take oral liquids.

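### The enrollment-suspension rule in Protocol 10.1.7 names an eye event, retinal vein detachment, that exists nowhere else in the plan; retinal detachment was most likely meant

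*Protocol*

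**What the plan says.** Protocol Section 7.1 sends the reader to Section 10.1.7 for the enrollment rule: "Conditions upon which the Sponsor will suspend additional enrollment in the study are described in the specified stopping criteria in Section 10.1.7". Section 10.1.7 opens its list with "Reasons which would cause the Sponsor to suspend/terminate enrollment include, but are not limited to, the occurrence of any of the following" and gives five bullets: one Grade 5 adverse event; two Grade 4 adverse events; one of several ocular toxicities; two large falls in ejection fraction or symptomatic heart failure; and one participant meeting the QTc stopping criteria.

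The ocular bullet begins "One occurrence of any of the following ocular toxicities: retinal vein occlusion" and continues "unexplained Grade 3+ Optic Neuropathy, Grade 3+ retinal vein detachment, or unexplained Grade 3+ retinopathy". It therefore has four items, and one occurrence of any of them is enough.

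The eye events of special interest in Protocol Section 8.3.1 (Table 10) include "Retinal detachment" as an entry of its own. SAP Section 4.2.1.1 (Table 8) has the same entry.

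**The concern.** A stopping criterion should name an event that can be recognized and reported. Retinal vein detachment is not defined in either document and is not used anywhere outside this bullet. Every other mention of a retinal vein event concerns occlusion. If the word vein was carried over from retinal vein occlusion earlier in the same bullet, the trigger meant for retinal detachment is not actually in the list.

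At stake is whether a single severe retinal detachment counts as a specified reason to pause enrollment or has to be inferred as one. Ocular toxicity is a known concern with this drug: Protocol Section 2.3 reports ocular disorders including retinal vein occlusion, mainly at doses of 10 mg twice daily or more, and the study enrolls children from age 2.

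**Working it through.** There is no figure in the plan to reproduce. The check is a comparison of terms, followed by a count of which criteria an event would meet.

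**Step 1. Match the ocular triggers to the eye events of special interest.**

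| Ocular item in Protocol 10.1.7 | Matching eye term in Protocol Table 10 and SAP Table 8 |
|---|---|
| Retinal vein occlusion | Yes |
| Optic neuropathy (Grade 3+, unexplained) | Yes |
| Retinal vein detachment (Grade 3+) | None; matches retinal detachment only if vein is removed |
| Retinopathy (Grade 3+, unexplained) | Yes |

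Three of four match. Table 10 has five eye terms: retinal vein occlusion, uveitis, optic neuropathy, retinopathy and retinal detachment. The two with no counterpart in 10.1.7 are uveitis and retinal detachment.

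**Step 2. Look for another event that could have been meant.** The only other detachment in the documents is in Protocol Appendix 12 (Section 10.12): "If a diagnosis of retinal pigment epithelial detachment or central serous retinopathy is made", dosing is held and may restart after resolution. An event managed by a hold and restart fits poorly as a one-event trigger for stopping enrollment. Retinal detachment is the better candidate, though the documents do not settle the matter.

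**Step 3. Count the bullets met by one retinal detachment with no other adverse event.**

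| Bullet in 10.1.7 | Grade 3, as written | Grade 4, as written | Grade 3 or 4, corrected |
|---|---|---|---|
| One Grade 5 event | No | No | No |
| Two Grade 4 events | No | No (only one) | No |
| Ocular list | No | No | Yes |
| Ejection fraction or heart failure | No | No | No |
| QTc | No | No | No |
| **Total met** | **0 of 5** | **0 of 5** | **1 of 5** |

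**Step 4. Check whether the retinopathy item already covers it.** It does not. Both tables list retinopathy and retinal detachment separately. The retinopathy trigger also applies only when the event is unexplained, a qualifier the detachment item does not carry. Folding one into the other would change the rule.

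**The case against.** The strongest reply is that the slip closes no route to a pause. The list is expressly open and the Sponsor may suspend the study at any time for any reason. The working safety steps do not use the faulty phrase:

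- Sites report eye events of special interest of Grade 2 or higher within 24 hours, regardless of relationship, under Table 10, which has the right term.
- Dosing for related events follows Table 4 (Section 6.6), whose ocular row "Any Grade ≥ 3 event except RVO" interrupts treatment.
- The monitoring committee has its own charter, and Section 9.5 says "Reviews will include aggregate safety, targeted medical events of special interest".

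A sensible reader would probably take the item to mean retinal detachment, and nothing in the documents suggests anyone would read it otherwise. The counts above describe a wording mismatch; they do not measure risk to participants. The intended event is also an inference.

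All of this stands as a limit on the importance of the point. It does not make the criterion correct. Section 7.1 presents the list as specified criteria on which enrollment will be suspended, and discretion to pause is different from a named trigger being met.

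**Conclusion.** The criterion is wrong as written, and the defect is minor. One of the four ocular triggers names an event found nowhere else in the plan, and a lone Grade 3 or Grade 4 retinal detachment consequently meets none of the five listed criteria when the text is followed literally. Enrollment could still be paused at the Sponsor's discretion.

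That the term is wrong rests on the text alone. That retinal detachment was intended rests on the other three items mirroring the event tables and on the poor fit of the only alternative. This is very likely but needs the Sponsor's confirmation.

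**What to change.** In Protocol Section 10.1.7, have the Sponsor confirm the intended event and change the item to Grade 3+ retinal detachment. Protocol Table 10 and SAP Table 8 already use that term and need no change.

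The edit deletes one word. Under Protocol Section 10.1.1, amendments go to the ethics committee for approval, so it is reasonable to make the correction in the next amendment and not to open one for this alone.
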